17. ASSESSMENTS

Research team members will conduct fortnightly home visits for:

17.1. Safety Monitoring

This will include collection of routine clinical bloods, assessment of LTAD and collection of LTAD drainage data collated by community nurses (see community SOP for sample drainage diary). LVP drainage data will be collected from medical records.

17.2. Patient Related Outcome Measures (PROMs)

Questionnaires will be completed online if possible (on smart phones), prompted by the fortnightly home visits by the research team members. Participants will also have the option to complete the questionnaires via phone. In those randomised to the LVP group, the questionnaires and fortnightly bloods could also be done in hospital if the LVP visit coincides with assessment visit (+/- 3 days). To further reduce patient and caregiver burden, research team members can assist the participants in completion of the questionnaires if needed and if specifically requested by the participant. If participants are too unwell, the questionnaires can be filled by proxy by the informal caregivers/research team members, both to reduce the patient burden as well as reduce risk of missing data. However, the aim will be to minimise proxy scores if possible. As far as possible informal caregiver is not available during the participant home visit, the questionnaires can be completed at a date and time which is convenient to them, online or over the telephone.

Questionnaires to be used:

SFLDQoL: Liver specific HRQoL assessed at baseline and every four weeks (+/- 3 days). It incorporates a core quality of life assessment and disease-targeted items transformed into the following nine domains on a scale of 0-100 (higher score - better quality of life): distress, stigma, memory, symptoms, sleep, hopelessness, effect of liver disease, loneliness and sexual function. (32) This is completed by the patient and takes 15-20 minutes to complete. Though there was a low completion rates in the feasibility study regarding sexual function questions, this data is important and will still be collected. The research teams will however ensure that questions on sexual function do not need to be answered, if patients feel uncomfortable or reluctant to answer them.

Ascites Q: Ascites symptoms assessed at baseline and fortnightly (+/- 3 days). It is validated in patients with ascites due to cirrhosis. It is a 11-item questionnaire (abdominal pain, fullness, loss of appetite, satiety, nausea, shortness of breath, back pain, mobility, fatigue, sleeping issues, size of abdomen). Each symptom is assessed with a frequency (6-point Likert scale "never" to "always") and discomfort (5-point Likert scale "not at all" to "a lot") question. A higher score indicates more symptoms. (74) This is completed by patients and takes 5-10 minutes to complete.

CRRS: Caregiver impact assessed at baseline and every four weeks (+/- 3 days). This tool measures the impact of caregiving on the other roles and responsibilities an individual has (finances, work, and social commitments), higher scores indicating better outcomes. The CRRS also captures any positive outcomes, such as benefit finding, that may come from caregiving. (75) This is completed by informal caregivers and takes 5-10 minutes to complete.

Modified AHCR: Primary, community and home-based health, social and voluntary service use will be assessed at baseline and fortnightly (+/- 3 days). The AHCR asks for the number of contacts in and out of the home with professionals or services, and informal caring input

(unpaid by family or friends), recorded as hours per day (on average). It will be administered by research team member during home visits, ensuring low rates of missing information. (76-77) This is completed by the patient and takes about 10 minutes to complete.

In-house designed hospital use questionnaire: hospital use related to all ascites and nonascites liver related treatment will be extracted at each site at the end of the study from patient hospital records and transferred onto a bespoke proforma distinguishing outpatient, A&E, day case and overnight stays. Will be completed by research team members at each site

EQ-5D-5L: Generic HRQoL assessed at baseline and fortnightly (+/- 3 days). It has five dimensions (mobility, self-care, usual activities, pain/discomfort, and anxiety/depression), rated on a 5-point Likert scale (1= no problems to 5= severe problems/ unable), to produce a health profile for use in the economic evaluation. It also comprises a 20 cm vertical Visual Analogue Scale (VAS) with range 0 (worst) to 100 (best). Health profile responses will be used to compute a utility index for estimation of QALYs. (78-79) This is completed by the patient and takes 5 minutes to complete.

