8. BACKGROUND AND RATIONALE

Ascites is the most frequent cirrhosis complication and also the most common complication requiring hospitalisation (1-2); up to a third of these patients can become unresponsive/ intolerant to medication. (3-4) This results in the debilitating condition called refractory ascites, associated with intense pain and breathlessness. As per the International Ascites Club Criteria, refractory ascites is defined as (i) diuretic-resistant ascites (ascites that cannot be mobilized or the early recurrence of which cannot be prevented because of a lack of response to sodium restriction and diuretic treatment) and or (ii) diuretic-intractable ascites (ascites that cannot be mobilized or the early recurrence of which cannot be prevented because of the development of diuretic induced complications that preclude the use of an effective diuretic dosage). (5-6) In absence of a liver transplant, refractory ascites reduces average life expectancy to between 6-12 months. (3-4,7-8) However, most patients with advanced cirrhosis, including those with refractory ascites, are not candidates for liver transplantation, transjugular intrahepatic portosystemic shunt (TIPS) or the Automated Low Flow Ascites (ALFA) pump. (3-4, 7-10) Locally in Brighton, between 2013-2015, only 14% of patients with refractory ascites were listed/underwent fa liver transplant/underwent **TIPS**. (4)

The most common intervention for refractory ascites is hospitalisation every 10-14 days for palliative large volume paracentesis (LVP). This involves an abdominal drain insertion for up to six hours, removal of 5-15 litres of fluid and administration of intravenous human albumin solution. (9) A UK study indicated that from 2013-2015, of the 45,000 individuals dying from cirrhosis, a third required repeated LVP in their last year of life, costing the NHS > £21,000/ person. (11) During our Patient and Public Involvement (PPI) engagement, avoiding hospitalisation was seen as the overarching goal. Repeated hospital visits for LVPs were "unbearably painful" "devastating" and "traumatic" at a time when patients were coming to terms with the prospect of dying. Many also felt stigmatised in hospital.

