To mitigate against research home visits impacting HRQoL in group 2 and thus diluting effects between the two groups, a SOP for the research home visits has been developed. The SOP

will promote standardisation of all the researcher visits to ensure they are limited to research tasks.

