22.5. Participant Safety Monitoring

At each site an experienced research team member will visit ALL patients at home fortnightly for safety monitoring and questionnaire-based assessments. This will include assessment of abdominal pain, vital signs, LTAD and collection of routine clinical bloods (FBC, INR, renal/ hepatic profile and CRP). The research team member will collect ascites drainage data recorded by community nurses at each site. Please see SAFETY REPORTING (section 22) for adverse event reporting.

The research team member will follow guidance in the lone worker policy when conducting home/usual place of care visits.

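### Only LVP patients may complete follow-up questionnaires at a drainage admission, with no rule on before or after drainage, which ties some LVP-arm scores to one setting and one point of the drainage cycle

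*Protocol*

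**What the plan says.** The default is the same for both arms. Section 17 states: "Research team members will conduct fortnightly home visits for" safety monitoring and questionnaires. Section 22.5 says that all patients, with emphasis on all, are seen at home "fortnightly for safety monitoring and questionnaire-based assessments". Section 17.2 has the forms done online where possible, prompted by those visits, and adds: "Participants will also have the option to complete the questionnaires via phone".

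Section 17.2 then makes an exception for the LVP arm alone: "In those randomised to the LVP group, the questionnaires and fortnightly bloods could also be done in hospital if the LVP visit coincides with assessment" visits, with a window of 3 days either side. Nothing states whether a form completed at that admission precedes or follows drainage, and nothing requires the place of completion to be recorded with it.

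On the drainage cycle, section 8 describes "hospitalisation every 10-14 days for palliative large volume paracentesis (LVP"). Sections 8.2 and 16.1 describe LTAD drainage at home, usually 1-2 L at a time, up to three times a week.

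The SFLDQoL is due at baseline and every four weeks, and Table 1 gives its recall period as four weeks. The Ascites Q and EQ-5D-5L are due fortnightly, and no recall period is stated for either.

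Section 16.2 provides an SOP to "promote standardisation of all the researcher visits to ensure they are limited to research tasks". It is there to stop home visits themselves from affecting quality of life in the LVP arm. As described, it does not cover forms completed at a drainage admission.

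**The concern.** LVP patients go through a long cycle of filling and drainage, while LTAD patients are drained little and often. A form completed on admission for LVP will usually meet the patient with fluid re-accumulated. A form completed after drainage meets the patient at their most relieved. The option can fix some LVP-arm scores at one of these points, in hospital, and has no counterpart in the LTAD arm.

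The trial is open-label with patient-reported outcomes, so a difference in measurement conditions between arms can appear as a treatment difference. The Ascites Q is the most exposed, because it asks about fullness, pain, breathlessness, mobility and abdominal size, which drainage is meant to relieve. The EQ-5D-5L covers mobility and pain and feeds the QALYs. The setting may matter too, since section 8 reports that the patient group found repeated hospital visits for LVP traumatic. The point concerns follow-up visits only.

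**Working it through.** **1. The plan's own figure.** Inputs from section 23.1: difference 8, SD 26.1 (effect size given as 0.31), correlation 0.48, three follow-ups, 5% significance (two-sided assumed), 90% power.

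- ANCOVA factor for the mean of three follow-ups: (1 + 2 × 0.48)/3 − 0.48² = 0.6533 − 0.2304 = 0.4229.
- n per arm = 2 × ((1.960 + 1.282)/0.31)² × 0.4229 = 92.5, so 93. The unrounded 8/26.1 gives 94.6, so 95.
- 186/(1 − 0.40) = 310.

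The sample size reproduces and is not in dispute. It implies a standard error of 26.1 × √(2 × 0.4229/93) = 2.49 points, used below for scale only.

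**2. How often the option is available.** The window of 3 days either side covers 7 calendar days. LVPs are at least 10 days apart, so a window holds at most one. With random phase, the share of assessments with an LVP in the window is 7 ÷ cycle length:

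- 14-day cycle: 7/14 = 50%.
- 10-day cycle: 7/10 = 70%.
- Over six fortnightly assessments: 6 × 0.50 = 3.0 to 6 × 0.70 = 4.2 per patient.

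Phase need not be random, because the LVP arm is drained at baseline (section 16.2):

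- A regular 14-day cycle from baseline puts an LVP on days 28, 56 and 84, so the share is 100%.
- A simulation of irregular intervals, uniform on 10-14 days and counted from baseline, gives about 43%, 49% and 66% at weeks 4, 8 and 12.

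These are shares eligible for the option. The protocol gives no uptake.

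**3. Recall.** Four weeks spans 28/14 = 2 to 28/10 = 2.8 drainage cycles. An SFLDQoL score therefore nominally covers whole cycles, and the day of completion acts only through how the current state colours recall.

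**4. Size, by assumption only.** The protocol gives no score gap between a form completed at drainage and the cycle average. Let s be the share of LVP forms completed at drainage (eligibility × uptake) and g the assumed gap in SFLDQoL points, all forms being on the same side of drainage. The arm difference then shifts by s × g.

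| s | g | Shift | Chance of significance with no true effect | Power for 8 points if the shift works against LTAD |
|---|---|---|---|---|
| 25% | 2 | 0.5 | 5.5% | 85% |
| 25% | 4 | 1.0 | 7% | 80% |
| 50% | 2 | 1.0 | 7% | 80% |
| 50% | 4 | 2.0 | 13% | 67% |
| 70% | 2 | 1.4 | 9% | 76% |
| 70% | 4 | 2.8 | 20% | 55% |

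Without a shift, power at 93 per arm is 89.5%. The standard error of 2.49 belongs to the mean of three follow-ups. For week 12 alone the same formula with factor 1 − 0.48² = 0.7696 gives 26.1 × √(2 × 0.7696/93) = 3.36, so the inflation in the fourth column would be smaller there. Because of the recall period, low values of g are the more plausible for the SFLDQoL. No corresponding figures can be given for the Ascites Q or EQ-5D-5L.

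**The case against.** The strongest reply is that the primary outcome is largely protected. The SFLDQoL looks back four weeks, and domains such as stigma, memory and loneliness have no obvious link to fluid volume on the day. This stands. A reader might infer that the primary comparison sets a cycle-averaged LTAD score against an LVP score fixed at one phase; the recall period does not support that.

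The option is also permissive, with home, online and phone completion open to both arms. This stands too: 50-70% is availability, not use.

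A reader might further infer that the bias favours LTAD, since patients come to LVP when full. The protocol does not say that the form precedes drainage, and completion afterwards would reverse the sign. If practice varies by site, the net effect could be near zero. This limits any claim about direction, but an unfixed order remains a weakness.

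Nor do the documents support saying that the analysis cannot examine the problem. LVP drainage data come from medical records at every visit (Table 3, section 17.1), and LTAD drainage is kept in a diary (section 16.1).

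Section 17.2 can fairly be read as a specific exception to the general statement in section 22.5, so that mismatch is minor. Finally, the option reduces burden in a palliative trial expecting 40% attrition, with questionnaire completion among the stop/go criteria. The fix has to respect that.

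**Conclusion.** The point holds as a correctable design weakness. Section 17.2 creates a measurement condition that exists in one arm only. It is available for roughly half to 70% of LVP-arm assessments under random phase, and for all of them on a regular 14-day cycle from baseline, with no rule on order relative to drainage. These shares rest on the 10-14 day interval in section 8.

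Direction is unknown: forms before drainage would favour LTAD and forms after it would favour LVP. The size cannot be derived from the protocol, and the shifts tabulated above rest on assumed gaps and uptake. The effect on the SFLDQoL is probably damped. The exposure is mainly in the Ascites Q, the EQ-5D-5L and the QALYs, although their recall periods are not stated, so how much more exposed they are cannot be shown. The documents do not support a conclusion that the primary result will be biased, or biased towards LTAD. The change is cheap and should be made.

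**What to change.** - In section 17.2, keep the hospital option for bloods. Have questionnaires in both arms completed at the home visit, online or by phone, within the existing window of 3 days either side and not during a drainage admission. Insisting on the nominal date would be too strict, since on a 14-day cycle that date can itself be an LVP day.
- As a fallback, where hospital completion is the only way to avoid a missing form, allow it under one fixed order relative to drainage, the same at all sites. Record the place of completion.
- Derive days since last drainage from the LVP records and LTAD diaries. Add a sensitivity analysis of the week-12 SFLDQoL, Ascites Q and EQ-5D-5L comparisons that accounts for forms completed at an LVP admission. One way is to shift those scores by a range of constants, as section 23.5 already does for missing outcomes. Simply dropping them would be a post-randomisation exclusion in one arm. The intention-to-treat primary analysis stays as it is.
- Reconcile section 22.5 with section 17.2 on where questionnaires are completed.

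The cost is a wording change, one recorded item and one sensitivity analysis. LVP patients lose some convenience, and there is a small risk of more missing forms, limited by the fallback. The change does not remove phase entirely: a form completed at home the day before an LVP still meets the patient near their fullest. Days since drainage would make that visible. Sample size and clinical care are unaffected.

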8.6. Assessment and Management of Risk

Research involving vulnerable adults in research is essential to generate high quality evidence. (66) Factors considered when planning this research and strategies instituted are:

Emotional distress exacerbated by the demands of the research

Written participant informed consent, communication skills and consenting vulnerable adults training for clinicians and research staff. Participants will have the right to withdraw from the study at any time without prejudicing routine clinical care.

Burden of data collection on the patient

Research team members will collect data during home visits to minimise burden and support the process. Questionnaire data can be collected in a variety of formats to suit participant needs. Proxy scores will be allowed, i.e. informal caregivers and research team members can help patients to complete the questionnaires.

Gate-keeping by staff

Gatekeeping is when healthcare professionals (HCP) or other involved parties prevent eligible patients from entering a trial as a research subject. (67) Training and support will be offered to all staff involved in recruitment to address the issue of gatekeeping.

Communications skills training

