9.4. Primary endpoint/outcome

The primary outcome is liver specific HRQoL assessed at 3 months using the SFLDQoL questionnaire (34), the only HRQoL tool validated in advanced cirrhosis.

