15.3. Implementation

Randomisation will be implemented using Sealed Envelope[™]. Patients will be enrolled by the research team who will log into the web-based system, enter patient ID number, recruiting site, gender and Child-Pugh Score. The system will automatically generate a confirmation email informing the research team of the allocation, a copy being sent to the BSCTU.

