15.4. Blinding

Due to the nature of the intervention, there can be no blinding in this trial except of the trial statistician who will be kept blind until completion of the analysis by means of dummy labelling of the trial groups.

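### When a participant is too unwell, section 17.2 lets research staff who know the allocation supply answers to the primary questionnaire, while section 8.6 describes proxy only as help

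*Protocol*

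**What the plan says.** Section 9.4 defines the endpoint: "The primary outcome is liver specific HRQoL assessed at 3 months using the SFLDQoL questionnaire". Section 17.2 first allows staff to assist with questionnaires when the participant asks. It then adds a separate permission for participants who are too unwell: "the questionnaires can be filled by proxy by the informal caregivers/research team members". The reasons given are patient burden and missing data. The next sentence is the only limit on use beyond the participant being too unwell: "However, the aim will be to minimise proxy scores if possible".

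The protocol describes the same matter differently elsewhere:

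- Section 8.6: "Proxy scores will be allowed, i.e. informal caregivers and research team members can help patients to complete the questionnaires".
- Section 17.2, on the SFLDQoL itself: "This is completed by the patient and takes 15-20 minutes to complete".
- Table 1 in section 8.1 lists the instrument as self-administered.

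On knowledge of allocation, section 15.4 states that "there can be no blinding in this trial except of the trial statistician", and section 15.3 that "The system will automatically generate a confirmation email informing the research team of the allocation". Sections 17.1 and 22.5 have the research team assess the LTAD at the fortnightly home visits at which the questionnaires are also prompted.

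**The concern.** The trial is open-label, and a patient's own knowledge of the allocation cannot be avoided. A staff member's judgement in place of the patient's answer can be. Several SFLDQoL domains (distress, stigma, hopelessness, loneliness) are internal states, and Table 1 gives a recall period of four weeks. A fortnightly visitor has little direct view of these. An impression of the patient, or of the drain just inspected, could fill the gap.

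Occasions for proxy completion are foreseeable. Section 14.2 expects capacity to fluctuate and provides for participation to continue after capacity is lost. It also admits patients without a caregiver, for whom staff would be the only proxy available. Table 6 sets completion targets for the SFLDQoL without saying whether a staff-answered form counts.

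Two things are at stake. Observer bias could enter the primary outcome in the sickest participants. And with 35 planned sites and two descriptions of proxy, staff at one site might only transcribe while staff at another supply answers.

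**Working it through.** **1. What the passages permit, side by side**

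| Place | Who answers the SFLDQoL |
|---|---|
| Table 1 (section 8.1) | Patient, self-administered |
| Section 8.6 | Patient, with help; this is called proxy |
| Section 17.2, assistance sentence | Patient, with staff help on request |
| Section 17.2, proxy sentence | Caregiver or research staff, if the patient is too unwell |
| Section 17.2, SFLDQoL paragraph | Patient |

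Because section 17.2 treats assistance separately, its proxy sentence must mean more than help. It therefore goes further than section 8.6.

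**2. How such a score would be treated**

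Section 23.4 analyses all collected data on all randomised participants. The MNAR work in section 23.5 imputes missing outcomes and then shifts them. A staff-answered form is not missing, so that work leaves it unchanged.

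**3. The plan's own figure, to obtain a standard error**

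Inputs from section 23.1: SD 26.1, difference 8, correlation 0.48, three follow-ups, 90% power, 5% significance (two-sided assumed), 93 per group, 40% attrition. I apply 0.48 to the correlation between follow-ups as well.

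- Variance factor for the mean of three follow-ups adjusted for baseline: (1 + 2 × 0.48)/3 − 0.48² = 0.653 − 0.230 = 0.423.
- n per group = 2 × (26.1 × √0.423 × (1.960 + 1.282)/8)² = 94.6, so 95. With the rounded effect size 0.31 it is 92.5, so 93, as stated.
- 186/(1 − 0.40) = 310, as stated.
- SE of the group difference at 93 per group: 26.1 × √0.423 × √(2/93) = 2.49 for the mean of three follow-ups; 26.1 × √(1 − 0.48²) × √(2/93) = 3.36 for week 12 alone.

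**4. Illustration of the shift (assumed inputs)**

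The protocol gives neither the share of staff-answered forms, p, nor the number of points, b, by which staff would favour one arm. With the same share in both arms, shift = p × b. Type I error = P(Z > 1.96 − shift/SE) + P(Z < −1.96 − shift/SE).

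| p | b | Shift (points) | Share of 8 | Type I error, SE 2.49 | Type I error, SE 3.36 |
|---|---|---|---|---|---|
| 5% | 5 | 0.25 | 3% | 5.1% | 5.1% |
| 10% | 5 | 0.5 | 6% | 5.5% | 5.3% |
| 10% | 10 | 1.0 | 12.5% | 6.9% | 6.0% |
| 20% | 10 | 2.0 | 25% | 12.7% | 9.2% |
| 25% | 10 | 2.5 | 31% | about 17% | about 12% |

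A second route needs no favouritism. If proxies score 10 points lower than patients in both arms, but proxy use is 10% in one arm and 30% in the other, the shift is (0.30 − 0.10) × 10 = 2.0 points.

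**The case against.** The strongest defence is that this is a deliberate and limited trade-off. Proxies are confined to participants who are too unwell, the protocol aims to minimise them, and it gives its reasons. Barring staff would lose forms selectively among very ill people without a caregiver. Caregivers are unblinded too and may perform the drainage themselves (section 16.1), so barring staff does not remove the problem. Section 8.6 is a summary paragraph, and section 17.2 can be read as the operative text.

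Much of this stands. The two limits belong in any fair statement of the point, and the caregiver argument is why the sensitivity analysis should cover all proxies. It does not remove the core: an aim to minimise is not a rule about who may answer, and two unreconciled descriptions of proxy remain for the primary endpoint.

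Three stronger readings are tempting, and the protocol does not support them:

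- *That proxy scores go unrecorded and undistinguished in the analysis.* The protocol is silent on this. It defers detail to an SAP, and neither that SAP nor the questionnaire layout was among the documents read. Either may already flag the respondent or include a sensitivity analysis.
- *That proxy use will rise towards week 12 or differ by arm.* No data are given. With 40% expected attrition, many of the sickest may have left by then, and all participants receive home visits.
- *That the bias favours LTAD by a known amount.* Neither size nor direction can be derived.

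**Conclusion.** The point holds as a fault in a stated rule. Allocation-aware staff who also assess the drain may supply answers to the primary questionnaire for participants who are too unwell, and the protocol describes proxy in two ways that need reconciling. Any resulting observer bias would sit in observed data, outside the reach of the section 23.5 analyses.

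The size is unknown. Under the assumed 10-25% staff share and 5-10 point tilt it is 0.5-2.5 points, or 6-31% of the 8-point target, in either direction; at 5% and 5 points it is negligible. The sample size is unaffected. This is an inexpensive improvement that should be made. It does not show that the primary result would be biased.

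**What to change.** - **Section 17.2:** state that research staff may read out SFLDQoL items and transcribe the participant's answers, but may not supply answers.
- **Section 8.6:** align its description of proxy with section 17.2.
- **Every questionnaire:** record the respondent (self, self with help, caregiver proxy, and staff proxy if retained), and report proxy use by arm and visit.
- **Analysis:** unless the SAP already does so, add one sensitivity analysis of the primary outcome with proxy SFLDQoL scores set to missing. This covers caregiver proxies as well.

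The cost is a few sentences, one data field, one descriptive table and one further model run. The downside is a few more missing forms among very ill participants without a caregiver, for which section 23.5 already has methods. If the sponsor keeps staff proxies for that reason, the minimum is to flag them and exclude them in the sensitivity analysis. Unlike the sensitivity analysis, which can be added until the SAP is agreed, the respondent field has to be in place when the forms are filled in.
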